## Statistical Analysis Plan

*Sample size:* Prior to the study, we anticipated that our best intervention would increase the baseline immunization coverage by least 20% compared to the control group. Assuming up to a 20% exclusion rate, we calculated that a sample of size 175 per group would yield us 90% power at 5% level of significance for this outcome.

*Statistical analysis:* Baseline data across the three study groups was summarized using either median and interquartile range (IQR) or frequencies and percentages. Multivariable Poisson regression analysis was used to estimate adjusted immunization rates in the two test study groups with the control group as reference. To compare immunization coverage at enrollment and at the end of the study, the incidence rate ratio was calculated accounting for median patient days in the study and the number of subjects for each intervention group. Unadjusted immunization coverage for each study group was calculated with Poisson exact 95% confidence intervals. Multivariable Poisson regression analysis was used to estimate adjusted immunization rates in the two test study groups with the control group as reference. Comparison between groups for timeliness of immunization was calculated using the Fisher-exact test. Data analysis was performed using Stata Version 14 (StataCorp LLC, College Station, TX USA) or GraphPad Prism Version 6.05 (La Jolla, CA 92037 USA).

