## **Study Procedures**

An encrypted, cloud-based software platform developed by Royal Datamatics Pvt Ltd (RDPL), New Delhi, India was used for record keeping and delivery of automated mobile-phone reminders and compliance-linked incentives (Supplementary Figure 1). Any child 24 months or younger at the time of enrollment, with a mobile-phone in the household and the ability of their caregiver to provide written informed consent were considered eligible for this study. After obtaining written informed consent from the caregiver, basic demographic information, Global Positioning System (GPS)-location and caregiver's finger biometrics were collected. While the standard of care in this setting involves the use of written immunization records (cards and records at the local primary health center) and verbal notification of follow up visits, record keeping for all groups in this study, including the control group, was performed using the software platform. Eligible subjects were randomly assigned to one of three study groups: self-returns with software platform for record keeping (control), automated mobile-phone reminders alone, and automated reminders with compliance-linked incentives in the form of mobile-phone talk-time. At the time of enrollment, data on prior immunizations received by the child were obtained from government-issued immunization cards provided by the families. If cards were unavailable or lost, immunization records were verified using written records at the local primary health center. The government-run National Immunization program (Supplementary Table 1) provided and administered the immunizations. The date for the next scheduled immunization visit was provided at each follow up by the government staff and entered into the software platform by the field workers. Each follow up visit was also correlated with the scheduled return date (if recorded in the system) of the administered immunization. Since finger identification is unreliable in young children, the child's name along with their caregiver's fingerprint was used to ensure positive identification of individual children at every visit. The GPS coordinates (longitude and latitude) were also recorded at recruitment and at each follow up visit. All users (field staff and study team) were identified and logged onto the software platform using biometric identification. For the study groups receiving automated reminders, Short Message Service (SMS) in the local language (Hindi) were sent. At follow up visits, mobile-phone minutes equivalent to INR 30 (~USD 0.5) per completed immunization were provided in the compliance-linked incentives group. The amount of incentive was determined after input from the local investigators as well as the community workers. All data transfers and compliance-linked incentives transactions were automated and occurred in real-time.

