
## **Randomization and masking**

Randomization was stratified by group (young children or pregnant) using a block randomization algorithm (block size of six), but in the current manuscript, only data for children is presented. All caregivers were informed of their child's group assignment and study field staff had access to group assignments for individual patients at the time of recruitment or follow up visits; however, all other study team members were blinded to the group assignments until the end of the study and after analysis of the blinded groups.

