## **End Points**

Immunization coverage was the primary outcome of the study and was calculated for each child as the proportion of the total number of immunizations received divided by the total number of immunizations required at the time of measurement (i.e. at enrollment, end of study, etc.). We also calculated the cost in mobile-phone messaging and compliance-linked incentives. Timeliness of immunizations was a secondary outcome measure and was defined as the proportion of immunizations administered before or within 14 days after the scheduled date recorded during the study.

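### The Poisson analysis of a per-child coverage proportion names no robust variance, covariates or offset, so its standard errors can be too small or too large

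*Combined protocol and SAP*

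**What the plan says.** End Points makes coverage the primary outcome and computes it for each child as the "total number of immunizations received divided by the total number of immunizations required at the time of measurement".

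The Statistical Analysis Plan compares the arms in one sentence, which appears twice: "Multivariable Poisson regression analysis was used to estimate adjusted immunization rates in the two test study groups with the control group as reference". Neither occurrence names a covariate, an offset or a variance estimator. The nearest exposure wording, median patient-days and number of subjects, belongs to the enrolment-versus-end comparison and works at group level. For the groups themselves, "Unadjusted immunization coverage for each study group was calculated with Poisson exact 95% confidence intervals".

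Two natural baseline predictors are available. Under Study Procedures, "data on prior immunizations received by the child were obtained from government-issued immunization cards", with health-center records as the fallback, and eligibility covers "Any child 24 months or younger at the time of enrollment". Randomization was stratified only by child versus pregnant woman, so neither age nor enrolment doses is a stratum.

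**The concern.** A Poisson model sets the variance of a count equal to its mean. Two features of this outcome break that equality, in opposite directions. Doses received cannot exceed doses required, which shrinks the variance. One caregiver's behaviour can drive several of a child's doses, which inflates it. Which feature wins depends on quantities that the documents do not give.

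There is a second consequence. Because plain Poisson variance is tied to the mean, its standard error hardly moves when a strong baseline predictor enters the model, even if the estimate itself becomes much more stable. Pre-randomization doses are part of the end-of-study numerator, so enrolment doses should predict that outcome well.

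At stake are the confidence intervals and p-values of the primary outcome. As written, their validity cannot be judged.

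**Working it through.** **1. The plan's own figure.** The sample-size paragraph reads "Assuming up to a 20% exclusion rate, we calculated that a sample of size 175 per group". No baseline coverage is given, so 175 cannot be reproduced from stated inputs alone. With an assumed 40% against 60%, two-sided 5% and 90% power, n = (1.960 x 0.7071 + 1.2816 x 0.6928)^2 / 0.2^2 = 129.3. The continuity correction gives 139.1, rounded up to 140, and 140/0.8 = 175. That match rests on a guess about a binary outcome. The only figure used below is 175 x 0.8 = 140 evaluable children per arm.

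**2. Variance ratio without covariates.** Let a child have m required doses, coverage p and within-child correlation rho. With a log(required doses) offset,

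true variance / Poisson variance = (1-p)(1+(m-1)rho),

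and the actual size of a nominal 5% test is 2(1 - Phi(1.96/sqrt(ratio))). The ratio equals 1 only at rho = p/((1-p)(m-1)). With assumed m = 10, each cell shows the ratio and the resulting type I error:

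| p | break-even rho | rho = 0 | rho = 0.1 | rho = 0.3 | rho = 0.5 |
|---|---|---|---|---|---|
| 0.4 | 0.074 | 0.60, 1.1% | 1.14, 6.6% | 2.22, 18.8% | 3.30, 28.1% |
| 0.5 | 0.111 | 0.50, 0.6% | 0.95, 4.4% | 1.85, 15.0% | 2.75, 23.7% |
| 0.7 | 0.259 | 0.30, 0.03% | 0.57, 0.9% | 1.11, 6.3% | 1.65, 12.7% |

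A beta-binomial simulation (140 per arm, 5-20 required doses, 5,000 runs per setting, same p and rho) gave 0.04% to 37% for plain Poisson and 4.6% to 5.9% for sandwich variance. If the proportion itself is the Poisson outcome with no offset, the ratio is divided by m. Type I error then stays below 0.4% for m of 10 or 20 and rho up to 0.7, which is over-conservative.

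**3. Adding enrolment covariates, cumulative outcome.** Assumptions, none from the documents unless stated:
- 14 doses, due at day 0 (3), 45 (3), 75 (2), 105 (3), 270 (2) and 500 (1).
- Enrolment age uniform over 0-6, 0-12 or 0-24 months.
- Per-child uptake beta(1.2,2.8), (2,2), (2.8,1.2) or (20,20); catch-up probability 0.1, 0.3 or 0.6; uptake shared or independent before and after enrolment. That makes 3 x 4 x 3 x 2 = 72 scenarios.
- Follow-up uniform over 159-374 days, from the document's dates (11 February 2017 and 11 July 2016, each to 20 July 2017).
- 140 per arm, no effect, 1,000 runs per scenario. Covariates: doses received, doses required and age at enrolment.

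In the central scenario (beta(2,2), catch-up 0.3, 0-24 months, shared uptake), for the log rate ratio:

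| | Unadjusted | Adjusted |
|---|---|---|
| Sampling SD | 0.0386 | 0.0213 |
| Plain Poisson SE | 0.0409 | 0.0411 |
| Robust SE | 0.0394 | 0.0210 |

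The variance falls by 1 - (0.0213/0.0386)^2 = 70%. The plain SE does not register this: 0.0411/0.0213 = 1.93 times the sampling SD.

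Over all 72 scenarios:
- Unadjusted plain 95% intervals covered 83-100% (below 93% in 12 scenarios, above 97% in 43).
- Adjusted plain intervals covered 98-100%, with SE 1.1-2.8 times the sampling SD.
- Adjusted robust intervals covered 93-96%.
- Adjustment cut the variance by 24-85% (median 54%).
- In three-arm runs, exact Poisson intervals for each group's coverage contained the truth 83-100% of the time.

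**4. Where the adjusted result turns round.** In a low-uptake setting, plain Poisson adjusted for age alone rejected 15% of the time at nominal 5% (400 runs, Monte Carlo SE sqrt(0.15 x 0.85/400) = 1.8 points). With on-study doses per day and all three covariates, it rejected 7% in a low-uptake setting. With SE sqrt(0.05 x 0.95/400) = 1.1 points at nominal, that run alone is weak evidence. Across the 72 scenarios, however, adjusted plain intervals for that outcome covered 91-99%, and 91% at 1,000 runs (SE 0.7 points) is clearly below nominal.

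**5. Precision if only on-study doses are counted.** Variance reduction was about 0-65% (median 33%) with a days offset and about 0-67% (median 14%) with an open-doses offset. In the central scenario it was 26% and 13%.

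**The case against.** The best reply is that this is partly a reporting gap. The plan calls the model multivariable and the rates adjusted, so covariates were used, and robust variance may have been used too. That stands: the documents do not show that these choices were absent. It does not cover the group coverage intervals, where the exact Poisson method is stated outright.

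Next, every calibration figure rests on assumed schedules, ages and uptake, and most scenarios err on the conservative side. That also stands. A reader might infer that this trial's false-positive rate is inflated, but the documents do not support any direction.

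A reader might also infer that an adjusted Poisson model is always too conservative. That held throughout the scenarios for cumulative coverage with enrolment doses in the model. It failed with age alone and with on-study doses per day. The plan speaks of rates and does not name the covariates, so which case applies is unknown.

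A third tempting inference is a large power gain. In the central scenario with an assumed true rate ratio of 1.10 and the cumulative outcome, power was 67% for plain unadjusted and over 99% for robust adjusted analysis. But the plan targets at least a 20% increase. At a ratio of about 1.20 in that scenario, all methods had essentially 100% power.

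Finally, a robust binomial or fractional-logit model would suit a bounded proportion as naturally. That is fair: keeping Poisson is a choice that stays close to the plan, and the essential part is variance at child level.

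**Conclusion.** The concern holds in a limited form, as something that should be changed, with medium confidence. Applied to this outcome, Poisson-based standard errors and intervals can be wrong in either direction, and the plan specifies nothing that protects against it. Naming a valid variance method is therefore more than a matter of missing detail.

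The error is conditional on the undisclosed covariates and on which dose count was modelled. The precision available from adjustment is likewise a range under assumptions, and it is nil if enrolment covariates and robust variance were already in use. Supplementary material was not available, so the point applies to the text provided.

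**What to change.** In the Statistical Analysis Plan, define the main between-arm analysis as one three-arm Poisson model:
- outcome: doses received by study end, with offset log(doses required at study end);
- child-level robust (sandwich) variance;
- adjustment for doses received at enrolment, doses required at enrolment and age at enrolment, each entered linearly. Entering the two counts, and not their ratio, keeps children with nothing yet required in the model.

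Use the same child-level robust variance for the group coverage intervals in place of the exact Poisson ones. If the analysis is complete, re-run it, label it post hoc and show it beside the existing result. If these choices were already used, state them.

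The cost is plan wording and a re-run on data already held, with no new visits. Downsides: robust intervals may cover slightly below nominal at this size, the linear covariate form is a modelling choice, and a post hoc re-run carries less weight than a prespecified one.

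### The before-after rate ratio on coverage is not a randomised comparison; efficacy should rest on end-of-study coverage between arms, adjusted for enrolment coverage

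*Combined protocol and SAP*

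**What the plan says.** End Points states that "Immunization coverage was the primary outcome of the study". It defines coverage for each child as doses received over doses required, "at the time of measurement (i.e. at enrollment, end of study, etc", which is an open list of times.

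The Statistical Analysis Plan then describes two comparisons of that outcome:

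- **Before-after.** The plan reads: "To compare immunization coverage at enrollment and at the end of the study, the incidence rate ratio was calculated". It then gives the inputs to this ratio, which it describes as "accounting for median patient days in the study and the number of subjects for each intervention group".
- **Between arms.** "Multivariable Poisson regression analysis was used to estimate adjusted immunization rates in the two test study groups with the control group as reference". This sentence appears twice. Neither occurrence gives a time point or lists the adjustment variables.

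The sample-size paragraph anticipates that "our best intervention would increase the baseline immunization coverage by least 20% compared to the control group". No sentence calls either comparison primary, and no between-arm test of change from enrolment is described.

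**The concern.** Randomisation protects the comparison of test groups with control. It does not protect a comparison of a group with its own past. Between enrolment and the end of the study children grow older, more doses fall due, calendar time passes, and every family takes part in the trial. Any of these can move coverage in all three arms with no contribution from reminders or incentives.

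What is at stake is how a before-after ratio in a test group would be read. Set beside the controlled analysis without a label, it could be quoted as evidence that the intervention raised coverage, which it cannot show. The between-arm model could also be sharper than described, because the plan does not say that it uses each child's coverage at enrolment.

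**Working it through.** **1. The plan's own figure.** The stated size is 175 per group, for 90% power at the 5% level with up to 20% excluded.

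- Evaluable per group: 175 × (1 − 0.20) = 140.
- The control rate, the scale of the 20% and the sidedness are not given. Assume 0.40 against 0.60 (20 points absolute), two-sided 5%.
- Uncorrected n = [1.96·√(2·0.5·0.5) + 1.2816·√(0.4·0.6 + 0.6·0.4)]² / 0.20² = (1.386 + 0.888)² / 0.04 ≈ 129.3, rounded up to 130.
- With continuity correction: (129.3/4)·[1 + √(1 + 4/(129.3·0.20))]² ≈ 139.1, rounded up to 140. Then 140/0.8 = 175.
- Assumed control rates of 0.35 or 0.45 give 138, and 138/0.8 = 172.5, rounded up to 173.

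The size is therefore compatible with a two-group comparison against control. That agrees with the wording of the sample-size sentence, though the match depends on assumed inputs and does not prove how the figure was obtained.

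**2. What each analysis estimates.** Let S be the change in coverage from enrolment to end that all arms share, as a ratio, and T the true effect of a test intervention, as a ratio. With equal coverage at enrolment:

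- before-after ratio in control = S
- before-after ratio in a test group = S × T
- end-of-study ratio, test against control = (S × T)/S = T

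The before-after ratio equals the effect only if S = 1.

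**3. Numbers put in (assumed rates, the 0.40 and 0.60 of step 1).**

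| | Test, enrolment to end | Control, enrolment to end | Before-after, test | Test against control at end |
|---|---|---|---|---|
| Full effect, no shared change | 0.40 to 0.60 | 0.40 to 0.40 | 0.60/0.40 = 1.50 | 0.60/0.40 = 1.50 |
| No effect, shared rise | 0.40 to 0.60 | 0.40 to 0.60 | 0.60/0.40 = 1.50 | 0.60/0.60 = 1.00 |

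The before-after column cannot tell the two rows apart. Smaller shared changes act in the same way: 0.35 to 0.45 gives 1.29 in every arm, 0.50 to 0.60 gives 1.20, and a fall from 0.60 to 0.50 gives 0.83. In each case the ratio against control is 1.00.

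**4. Is a shared change plausible here?**

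- Study Procedures: records for all groups, control included, were kept on the software platform, whereas usual care relies on written records and verbal notice.
- Authentication and follow up: caregivers in all three groups, control included, were given scripted return instructions at recruitment and at each visit.
- Automated reminders and compliance-linked incentives: doses received elsewhere could be added to the record in every group.
- Study design and participants: enrolment began on July 11, 2016, the target was met on February 11, 2017, and the study ended on July 20, 2017. If recruitment stopped at the target and every child was followed to the last date, follow-up runs from 159 to 374 days, in children aged up to 24 months at entry.

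A shared change is therefore credible. Its direction is not known, because doses required also increase with age.

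**5. Enrolment coverage.** Study Procedures says that prior doses were taken from immunization cards or health-centre records at enrolment. Those doses count in the enrolment numerator and again in the end-of-study numerator, so the two measurements on one child are linked by construction. This makes enrolment coverage a natural covariate. It also means that enrolment and end totals cannot be treated as independent counts. For that reason, and because the documents give no coverage or dose counts, no rejection probability is calculated here for the before-after ratio.

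**The case against.** The strongest reply is that the documents already point to the right contrast. Children are randomised to three groups with a named control, the only powered gain is against control, and the model that is to "estimate adjusted immunization rates in the two test study groups with the control group as reference" is stated twice. Timeliness is also compared between groups. Nothing powers the before-after ratio, tests it or sets a success rule for it. Enrolment cannot carry a treatment effect, so end of study is the evident efficacy time point despite the open list in End Points. All of this stands and keeps the point modest.

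It is also fair that the ratio sentence is loose. Its closing phrase may describe only the scaling inputs, and the ratios may have been meant for comparison across groups. In that case a between-arm test of change is needed, and none is described.

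A reader might go further and infer that the false-positive rate of an efficacy claim is well above 5%, for instance under a rule of significance in a test arm but not in control. The documents do not support this. They state no such rule, and any figure for it would rest on assumed rates and on treating two measurements of the same children as independent. A reader might also infer that the two analyses could give conflicting answers on the primary outcome. They would not: a rise over time with no difference between arms is a pair of compatible answers to two questions.

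**Conclusion.** The concern holds in a limited form. The randomised comparison is in the plan and is strongly implied to be the efficacy analysis. Beside it stands a before-after ratio that cannot separate an intervention effect from ageing, calendar time and trial participation, so it should carry no efficacy conclusion. As step 3 of the working shows, the same ratio of 1.50 fits both the full assumed gain and no effect at all.

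This rests on the within-group reading of the ratio sentence and on a shared change being possible, not on its being documented. The size of any misreading cannot be calculated from the documents. The practical gain lies in two better methods: adjusting the end-of-study comparison for enrolment coverage, and contrasting change between arms in place of change within arms.

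**What to change.** In the Statistical Analysis Plan:

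1. State that the efficacy conclusion on coverage rests on the comparison of each test group with control at end of study, using the Poisson model, with the child's enrolment coverage as a covariate.
2. In End Points, name end of study as the time point of the primary outcome. The general definition of coverage can stay for other uses.
3. Either replace the before-after ratio with a between-arm contrast of change (an arm-by-time term, with standard errors clustered by child), or report the enrolment-to-end ratios for all three arms as descriptive only.

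The cost is some wording and one more model term. Prior doses are already recorded at enrolment, so no new data or participants are needed. The one loss is that the before-after ratios can no longer be quoted as evidence of effect.

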## **Study design and participants**

We prospectively enrolled children 24 months and younger and pregnant women from a rural community in the Mewat region located within the state of Haryana, India from July 11, 2016 to July 20, 2017. Recruitment and follow up were performed concurrently, though the recruitment target was met on February 11, 2017. The study was administered by Bal Umang Drishya Sanstha (BUDS), a New Delhi based non-profit organization with a focus on child health. This study was approved by the Research Ethics Committees of BUDS, New Delhi, India and the Johns Hopkins University, Baltimore, MD, USA. This trial is registered with ClinicalTrials.gov, number NCT03180138.

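### The enrolment-to-end comparison of coverage uses an incidence rate ratio built on median study days and subject numbers, an exposure that does not fit coverage as the protocol defines it

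*Combined protocol and SAP*

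**What the plan says.** The End Points section makes immunization coverage the primary outcome. It is calculated child by child as the "proportion of the total number of immunizations received divided by the total number of immunizations required at the time of measurement", and enrolment and end of study are both named as measurement times.

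The Statistical analysis paragraph of the Statistical Analysis Plan then sets out the comparison of the two times. Its purpose is given as "To compare immunization coverage at enrollment and at the end of the study", and its method is that "the incidence rate ratio was calculated accounting for median patient days in the study and the number of subjects for each intervention group". Doses required are not named there as denominator, exposure or offset. The numerator is not given, nor is the exposure that applies at each time.

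Under Study Procedures, the enrolment figure rests on history: "data on prior immunizations received by the child were obtained from government-issued immunization cards provided by the families". Lost or unavailable cards were replaced by records at the local health center.

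The same analysis paragraph lists two further analyses. One is an interval for coverage in each group: "Unadjusted immunization coverage for each study group was calculated with Poisson exact 95% confidence intervals". The other is a multivariable Poisson regression comparing the two intervention groups with control.

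**The concern.** Coverage is a share of the doses due. Person-time is the denominator of a rate. The sentence takes the first as its target and names only ingredients of the second. The mismatch is plainest at enrolment, where every recorded dose precedes the study and no child has yet contributed a study day.

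What is at stake is how a reader interprets the stated before/after result for the primary outcome. Children enter at 24 months or younger and are followed while further doses fall due. A ratio above 1 could therefore mean that coverage improved, or only that the children grew older and received some of the doses that came due. As written, the plan does not let the reader tell these apart.

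**Working it through.** The plan reports no value for this ratio, so there is no figure to reproduce. The check is algebraic, with a small illustration. The vaccination schedule (Supplementary Table 1) is not in the text, so all dose counts below are assumptions.

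**Notation.** For one arm, R0 and R1 are total doses received by enrolment and by end of study, and Q0 and Q1 are total doses required at those times. N is the number of subjects and D the median study days. From the definition in End Points, pooled coverage is R0/Q0 at enrolment and R1/Q1 at end.

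**Step 1: study days taken literally.** At enrolment, days in the study are zero, so a rate per study day is undefined there. Some other exposure must have been used at enrolment, and the plan does not name one.

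**Step 2: cumulative dose counts, with the same N × D at both times.**

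(R1 / (N × D)) / (R0 / (N × D)) = R1/R0

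The exposure cancels. Multiplying and dividing by the doses required gives

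R1/R0 = [(R1/Q1) / (R0/Q0)] × (Q1/Q0)

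So the ratio equals the pooled coverage ratio multiplied by the growth in doses required. This identity needs no assumption about the schedule. For the same children, cumulative doses cannot decrease, so R1/R0 cannot be below 1 whatever happens to coverage.

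Illustration per child, starting from an assumed 4 received of 8 required:

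| End of study | Growth Q1/Q0 | Count ratio R1/R0 | Coverage ratio |
|---|---|---|---|
| 4/8 | 1.00 | 1.00 | 1.00 |
| 5/10 | 1.25 | 1.25 | 1.00 |
| 6/12 | 1.50 | 1.50 | 1.00 |
| 5/12 | 1.50 | 1.25 | 0.83 |
| 4/12 | 1.50 | 1.00 | 0.67 |

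In the fourth row coverage falls from 50% to 42%, yet the count ratio reads as a 25% rise. Check: 0.833 × 1.50 = 1.25.

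**Step 3: coverage itself as the numerator, with a common exposure.**

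[(R1/Q1) / (N × D)] / [(R0/Q0) / (N × D)] = (R1/Q1) / (R0/Q0)

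This is the coverage ratio, without error. N and D cancel and contribute nothing.

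**Step 4: which reading applies.** Poisson exact intervals for coverage in the same paragraph suggest that dose counts were the working numerator. They do not prove it, because that is a separate sentence about a separate quantity.

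**Step 5: a group median as person-time.** Even for a dose rate, N × D equals total person-days only if median and mean follow-up agree. Study design and participants states: "Recruitment and follow up were performed concurrently, though the recruitment target was met on February 11, 2017". The study dates, July 11, 2016 to July 20, 2017, span 374 days, and February 11 to July 20, 2017 is 159 days. If enrolment closed when the target was met, which is an inference, possible follow-up to the end date ran from 159 to 374 days. That is wide enough to prefer each child's own days to a group median.

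**The case against.** The strongest reply is that this is under-specification and not a wrong denominator. The sentence says that coverage is being compared, and coverage is already defined as received over required. Nothing says that doses required were left out, and on the reading in Step 3 the result is correct. Likewise, if the ratio compares arms at each time, randomization balances doses required on average and there is no systematic bias. This stands in part: an erroneous result is conditional on a dose-count numerator. It does not rescue the text, because the inputs it names are not those of the endpoint and on neither of these readings do median study days help to estimate coverage.

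A second reply is that the before/after contrast is secondary to the randomized comparison with control, and that coverage is also reported directly for each group. That is fair, and it limits the importance of the point.

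A reader might infer more than the documents support:
- **That the reported ratio is inflated.** This follows only under Step 2, and the numerator is unstated.
- **That age in days served as the enrolment exposure, so the ratio could be pushed below 1.** The plan speaks only of days in the study. Age as an exposure appears nowhere.
- **That the trial's between-group result is compromised.** The multivariable Poisson model is a separate analysis, and this point does not reach it.

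A further caution concerns the remedy. Summing doses over children is not the same quantity as coverage calculated for each child. Two children at 2/2 and 2/8 average (100% + 25%)/2 = 62.5%, whereas pooled coverage is 4/10 = 40%. The per-child measure should therefore come first.

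**Conclusion.** The point holds in limited form. The stated method for comparing the primary outcome at enrolment and end of study uses an exposure that does not belong to that outcome and that has not accrued at enrolment.

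If the numerator is cumulative doses with a common exposure, the ratio departs from the pooled coverage ratio by exactly the factor Q1/Q0. It can then move in the opposite direction to coverage, as in the illustration of 1.25 against 0.83. If the numerator is coverage, there is no error and the two named quantities are redundant. The documents do not settle which applies, so neither the size nor the direction of any error can be fixed. The identity is exact, but the example counts are assumed.

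This should be corrected, since it concerns a stated comparison of the primary outcome and a replacement is cheap. Confidence is moderate because the numerator is unstated.

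**What to change.** Remove median study days and subject numbers from this comparison, and state the numerator and denominator at each time.

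- **Main summary.** Compute each child's coverage (received/required) at enrolment and at end. Report by arm the mean within-child change with a paired or child-clustered 95% interval. State how many children had no doses required at enrolment and so cannot contribute.
- **Sensitivity analysis.** Report by arm the ratio of pooled coverage, that is, summed received over summed required at each time, or a Poisson model with log doses required as offset. Use child-clustered robust errors. Note that this weights children by doses required, and that a child with none required at enrolment enters only the end-of-study sums.
- **Label.** Call the by-arm change descriptive, because ageing and intervention are mixed in it.
- **Dose rate, if wanted.** Count only post-enrolment doses, over each child's own follow-up days.

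The cost is a change to the SAP wording and a small re-analysis. Prior doses, follow-up doses and visits are already recorded through the software platform. The price in information is that children with nothing required at enrolment drop out of the paired analysis.
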